Pentoxifylline Treatment in
Acute Pancreatitis: A Double-
Blind Placebo-Controlled
Randomized Trial

NCT 02487225

January 9, 2017

TITLE AND SUMMARY PAGE

Project Title: Pentoxifylline Treatment in Acute Pancreatitis; A Double-Blind Placebo-Controlled Randomized Trial

Principal Investigator:

[name] [name]
Section of Gastroenterology and Hepatology
Professor of Medicine
Mayo Clinic College of Medicine
[name]
[contact]
[contact]
[contact]

Participating Investigators:

[name].
[name].
[name]

Project Summary:

Background. Acute pancreatitis (AP) is a cause of significant morbidity and mortality and effective therapeutic regimens to treat this condition are lacking. Extensive experimental evidence indicates that tumor necrosis factor alpha (TNF- α) contributes to the pathogenesis of multiple organ failure (main cause of morbidity and mortality) in AP, suggesting a possible role for inhibition of TNF- α in the treatment of AP. There is no effective drug therapy for AP and hardly any human experience about the role of pentoxifylline in AP Methods: Randomized, double-blind, placebo-controlled study comparing three times daily dosing with Pentoxifylline from the time of admission until 72 hours of hospitalization in patients presenting with AP. Seventy-five patients will be enrolled in both the "treatment" and "placebo" groups (150 patients total). This study will be performed at Mayo Clinic, Rochester. Primary outcomes: Determine changes in CRP, TNF- α , IL-6, and IL-8 levels from admission baseline at one week.

Significance: If our hypothesis is confirmed this trial will be a landmark development in the treatment of AP. A simple, safe, and inexpensive drug that can be given to all patients with AP, in all settings, will be available to decrease the significant morbidity and mortality due to this disease.

PROJECT DESCRIPTION

Specific Aims:

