Aim1: Determine if oral pentoxifylline will improve clinical outcomes in AP. Persistent SIRS and organ failure, pancreatic and/or peripancreatic necrosis and infection (determinants) will be primary endpoints, while death (infrequent), length of stay, and the need for ICU and intervention will be secondary endpoints. These are all identified in the revised Atlanta classification as outcomes of interest. Hypothesis: Pentoxifylline will decrease the occurrence of any one of the following adverse outcomes in AP: pancreatic and/or peripancreatic necrosis and infection, persistent organ failure, prolonged hospital stay, need for ICU, and intervention and death in patients with AP.

Aim2: Determine if oral pentoxifylline will decrease serum levels of inflammatory markers.
Hypothesis: Pentoxifylline will reduce levels of CRP, TNF- α , IL-6, and IL-8, and this reduction will correlate with clinical outcomes in patients with AP.

Background and Significance:

Acute pancreatitis, an inflammation of the pancreas gland, is the most common gastrointestinal hospital discharge diagnosis and averages \$2.6 billion in costs per year. Yet, as common as it is, there is no specific drug to treat this disease. There has been no drug trial in AP since the beginning of this century. Based on previous animal studies and a pilot study in humans at our institution, pentoxifylline has shown to block the inflammation in this disease. A larger study must be performed before the efficacy of this drug can be confirmed. A successful study would provide a breakthrough in AP therapy, paving the way for a simple, safe, and inexpensive drug to be available world-wide to treat this disease. This novel approach would be a major advancement in the treatment of this disease.

Acute pancreatitis (AP) is a common inflammatory condition of the pancreas leading to the hospitalization of millions of patients annually worldwide. While the majority of patients (~80%) have mild, self-limiting disease with low mortality, severe acute pancreatitis (SAP) is associated with high morbidity and mortality (20-40%) and prolonged hospital stays. Specific pharmacological therapies, such as aprotinin, glucagon, gabexate, somatostatin and lexipafant, have not been shown to have any advantage in randomized controlled trials. As a result, treatment for AP is mainly supportive involving bowel rest, aggressive intravenous fluid resuscitation and pain control -a targeted therapy for AP is therefore urgently needed.

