2. Pentoxifylline reduces the blood levels of inflammatory markers, which correlates with improvement in clinical outcomes. This study is a novel, exploratory clinical study of the effect of a drug that has a proven role in animal studies in blocking the inflammatory response in AP. It is also a high reward study that will lead to a breakthrough in the treatment of AP and challenge the age old recommendation of supportive treatment alone.

The study will have 2 groups of 75 patients each, all with AP, randomly assigned to either the drug or a placebo, which looks like the drug, for a period of 3 days or until the time they are discharged, if hospital discharge is within 7 days of admission. The levels of markers of inflammation (CRP, IL-6, IL-8 and TNF- α) will be measured at baseline and on 5 successive days or until the time of discharge, whichever occurs earlier. Determination of group size was based on the previous pilot study to decrease any of the important adverse outcomes, providing for a dropout rate of 10% during the study. During 2012, 263 patients with AP were admitted to this institution, which possesses the needed infrastructure for successful completion of clinical drug intervention trials. In the stipulated period of 2 years by the NIH, the required number of patients for the study could be recruited.

This project represents a single center study at Mayo Clinic Rochester. The trial is a randomized, double-blind, placebo-controlled study design.

Subjects: Subjects will be adult patients 18 years of age and greater which will be recruited from Mayo Clinic and admitted to the hospital with acute pancreatitis as defined by at least two of the following:

- amylase and/or lipase greater than 3 times the upper limit of normal values,
- characteristic cross-sectional imaging,
- characteristic pain syndrome.

If patients give consent to be in the study the PI may contact those patients before formally enrolling them in the study. By overseeing that one of the team (a study coordinator, PI, and co-investigator) is present during the weekends, we anticipate that those eligible patients during the weekend period are not going to be excluded.

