Patients admitted within 24 hours with AP diagnosis will be included, with the exception of those meeting the exclusion criteria. Those patients that have been identified with AP diagnosis within 72 hours will be approached by the study coordinator and also by the principal investigator (PI) (whenever feasible) to explain the study and obtain written consent.

Inclusion criteria

- Enrollment within 72 hours of diagnosis of AP
- Ability to give informed consent or a legal adult representative LAR able to give informed consent for subject when needed as defined but LAR use guidelines.
- Adult subjects of age ≥ 18 years.

Exclusion Criteria:

- Moderate or severe congestive heart failure,
- History of seizure disorders or demyelinating disease,
- Nursing mothers,
- Pregnancy,
- History of prior tuberculosis or risk factors for tuberculosis
- Evidence of non- corticosteroid immunosuppression (such as malignancy, chronic renal failure, chemotherapy within 60 days, and HIV)
- Evidence of active hemorrhage,
- Paralytic ileus with severe nausea and vomiting.

Laboratory test and assessments:

Test / Procedure	Day 0	Day 1	Day 2	Day 3	Day 4	Day 5
TNF-a*	X	X	X	X	X	X
IL-6*	X	X	X	X	X	X
IL-8*	X	X	X	X	X	X
Pregnancy Test X						
CRP	X*	X*	X*	X*	X*	X*

* Note: The C-RP, TNF-a, IL-6, IL-8 tests are charged to the research study. All other tests listed are clinical standard care for acute pancreatitis.

The pregnancy test may be done as standard of care and will be closely monitored by study staff to assure completion before subject receives study medication.

Follow up process may be done by telephone contact or review of medical records dependant on subjects follow-up information availability. Some subjects may do their follow up visits at a

local facility not return to Mayo Clinic Rochester for follow up visit within the 4 month time frame (plus or minus 15 days). Thus their medical record may not be available in the Mayo Network system. Then a telephone contact may be done to acquire the follow up information.

Randomization:

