Randomization will be performed by the pharmacy under the direction of the study statistician, using randomized blocks, to ensure all clinical study personnel are blinded to patient allocation throughout the study. Subjects will be randomized into two groups. The "treatment group" will receive Pentoxifylline 400 mg one to three times daily by mouth from the time of enrollment until 72 hours from enrollment. Subjects will receive up to maximum of 9 doses of this medication. The "control" group will receive placebo dosing at similar intervals. Randomization will occur in a block fashion. Study medication will be administered at 1x/day if creatinine clearance \leq or \geq 30ml/min. per the manufacture prescribing information. All other treatment for AP (fluid resuscitation, antibiotics, surgical intervention, pain control, etc.) will be at the discretion of the primary care team. However, the study investigators will ask primary teams to follow standardized treatment guidelines for acute pancreatitis (to control for intravenous hydration and enteral nutrition, which may influence IL levels).

Blinding: Both subjects and investigators will be blinded to the randomization.

Sample Size:

We propose testing 75 patients in each study arm. Our primary outcome will be whether the patient develops any of the following outcomes of moderate or severe AP: hospital stay longer than 10 days, admittance to the ICU, persistent organ failure, pancreatic and/or peripancreatic necrosis and infection, SIRS, need for intervention, or death. In our pilot study, 7.1% of the patients on pentoxifylline experienced at least one of these outcomes, compared to 28.6% of those on the placebo. If extrapolated to the larger RCT, this reduction in events of these critical outcomes (7.1% vs. 28.6%) would represent a significant and meaningful difference for patients. Using a 5% 2-sided type I error, 58 patients in each group would be needed to achieve 80% power to detect the anticipated difference. In order to account for the unlikely event of up to 10% study dropout, we plan to enroll 64 patients in each group. We will use a randomized block design stratifying for predicted disease severity (mild, moderate, or severe).

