Data Collection and Handling: TNF- α , Il-6, and Il-8 will be handled by the research blood draw division of Mayo Clinic per usual practice. The C-RP testing on days 1, 3, 4 and 5 will be handled by the research blood draw division of Mayo Clinic per usual practice. The clinical and research laboratory data will be recorded every day until discharge. Early discharges before completion of 3 days of drug or 5 days of study of markers after drug administration is not considered as protocol violation and data until the time of discharge will be recorded for the purpose of analysis. Data Safety Monitoring Board (DSMB) will be constituted by clinicians having experience in TNF- α blockade therapy.

Data Analysis: All access to data will be password protected. Analysis will be on an-intent-to-treat basis. Outcomes will primarily be descriptive statistics such as means and percents. Continuous secondary end points will be analyzed with the t-test if the data are normally distributed and the Wilcoxon Rank Sum test if non-normal. Analyses of dichotomous secondary end points will use either the Chi-squared test or Fisher's Exact Test comparing proportions. Kaplan-Meier will be used to estimate survival. An interim analysis of data for preliminary review of less than target accrual may be done.

Feasibility: Nearly 250 patients with acute pancreatitis are seen at Mayo Clinic hospitals every year. Assuming ~60% of them are directly admitted to Mayo Clinic (not transferred from outside), and 50% agree to participate in the study it would take 24 months at Mayo to recruit 150 patients. If recruitment goals are not reached at Mayo Clinic after ~24months, the study may have to be extended for 6 months more. **Deliverables:**

We expect to publish at least one manuscript in a major academic journal as a result of this work. Our hope is that any reduction of morbidity or mortality from the novel therapy will have a profound effect on the treatment of acute pancreatitis and lead to future expanded clinical trials.

TAILED MILESTONES SCHEDULE

Endpoints:

May 2015 Mayo Institutional Review Boards (IRB) approval.

June 2015 Approximate NIH will release funds when IRB approved protocol is provided.

July 2015 - Approximate Patient enrollment begins at Mayo

April 2016 Approximate Data Safety Monitoring Board (DSMB) contact via teleconference or E-mail meeting to meet biannually and/or not less-than once a year.

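### The marker endpoint is set at one week, when no draw is scheduled; its role differs between sections, and no analysis rule covers patients discharged earlier

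*Combined protocol and SAP*

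**What the plan says.** All references are to the combined protocol and SAP.

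- **Role.** The Project Summary lists marker change as the primary outcome, ending "IL-6, and IL-8 levels from admission baseline at one week". Specific Aims makes clinical events primary and gives the markers their own aim ("Determine if oral pentoxifylline will decrease serum levels of inflammatory markers"), outside both the primary and the secondary endpoint lists. Sample Size states "Our primary outcome will be whether the patient develops any of the following outcomes of moderate or severe AP"; no marker is among the components, and the only power calculation is for that composite.
- **Day and baseline.** Experimental Design has markers taken at baseline and "on 5 successive days or until the time of discharge, whichever occurs earlier". The table under Laboratory test and assessments ends at Day 5. Day 0 is not defined. The Project Summary counts from admission, the inclusion criterion is "Enrollment within 72 hours of diagnosis of AP", and Randomization counts dosing "from the time of enrollment until 72 hours from enrollment".
- **Discharge.** Data Collection and Handling accepts early discharge and keeps the values obtained up to that point. Data Analysis asks for intent to treat. Neither says what happens to a patient with no draw on the endpoint day.
- **Tests.** "Continuous secondary end points will be analyzed with the t-test if the data are normally distributed and the Wilcoxon Rank Sum test if non-normal". No baseline covariate, stratum term or repeated-measures method is named, although randomisation is stratified by predicted severity and the daily assays are bought for the trial ("The C-RP, TNF-a, IL-6, IL-8 tests are charged to the research study").

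**The concern.** An endpoint whose role, scale and day are open can be settled after the data are seen, here across four markers. If the markers are primary, no inferential test is named for them at all, because the quoted sentence covers secondary end points only. If they are secondary, the natural use of that sentence is a two-sample test on one day. That test discards everyone already discharged, with all their earlier draws, and takes no advantage of the Day 0 value beyond what a change score does.

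Discharge is likely to be common. Background and Significance puts mild, self-limiting disease at about 80%, and the institution's own series under Significance had 31% moderate or severe. Patients who remain in hospital are a selected group, so a comparison of raw levels among them may also be biased.

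**Working it through.** **1. The plan's own figure.** Inputs from Sample Size: 28.6% v 7.1%, two-sided 5%, 80% power. The difference is 0.215 and the mean rate 0.1785.

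n' = [1.960√(2 × 0.1785 × 0.8215) + 0.842√(0.286 × 0.714 + 0.071 × 0.929)]² / 0.215² = 48.6

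With continuity correction, n = (n'/4)[1 + √(1 + 4/(n' × 0.215))]² = 57.5, so 58 per group, as stated. This concerns the composite. There is no marker calculation to reproduce.

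**2. Can the one-week endpoint be observed?**
- If Day 0 is admission, the last draw comes five days after baseline.
- If Day 0 is enrollment, 0 to 3 days after diagnosis, then Day 5 falls 5 + 0 = 5 to 5 + 3 = 8 days after diagnosis. A draw seven days after admission then needs enrollment two days after admission, and that patient's Day 0 is not an admission baseline.

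On neither reading does the schedule give one patient both an admission baseline and a one-week value.

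**3. Cost of testing only patients still sampled.** Detectable effect at 80% power = (1.960 + 0.842)√(2/n), in SD units. The shares still sampled are assumed. Sample Size gives both 75 and 64 per arm, so both are shown.

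| Still sampled | Detectable effect, 75 / 64 | Power for 0.5 SD, 75 / 64 |
|---|---|---|
| 100% | 0.457 / 0.495 | 86.5% / 80.7% |
| 75% | 0.528 / 0.572 | 75.5% / 68.8% |
| 50% | 0.647 / 0.700 | 58.1% / 51.6% |
| 25% | 0.915 / 0.991 | 33.4% / 29.3% |

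A longitudinal model recovers only part of this loss.

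**4. Value of baseline adjustment.** With equal SDs and baseline correlation r, relative variance is 2(1 − r) for a change score and 1 − r² after adjustment, a saving of (1 − r)/2. Power is for 75 per arm, complete data and a 0.4 SD effect.

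| r | Change | Adjusted | Saving | Power, change / adjusted |
|---|---|---|---|---|
| 0.3 | 1.40 | 0.91 | 35% | 54.4% / 72.8% |
| 0.5 | 1.00 | 0.75 | 25% | 68.8% / 80.7% |
| 0.7 | 0.60 | 0.51 | 15% | 88.5% / 92.9% |

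**5. Both together, by simulation.** Everything here is assumed except the 31% moderate or severe and the 75 per arm.
- Log-marker models: subject SD 0.8 with error SD 0.45; subject SD 0.7 with slope SD 0.15 per day and error SD 0.45; subject SD 0.4 with AR(1) error SD 0.8, correlation 0.7.
- Effect: −0.35, reached in thirds by Day 3 and then constant.
- Discharge: daily probability logistic in the marker state (observed or unmeasured) and arm, leaving 58-96 of 150 in hospital on Day 3 and 30-67 on Day 5.
- Size: 24 scenarios, 2,000 trials each.

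Mixed model (treatment, Day 0 value and stratum, each by day) against a change-score t-test on the same day:
- Day 3: variance 14-39% lower; power 25-82% v 21-75%. Baseline and stratum adjustment alone gives 8-33%; earlier draws cut a further 3-13%.
- Day 5: variance 17-44% lower; power 10-69% v 10-61%, a change of −3 to +14 points.

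A recode of 12 scenarios gave 12-37% and 16-44%. A simplified recode without strata gave 8-38% and 20-50%.

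**6. Bias on Day 3 (truth −0.35).**
- Raw levels: −0.29 to −0.34 with the same discharge rule in both arms, −0.17 to −0.26 with earlier discharge on drug, −0.38 to −0.41 with later discharge on drug.
- Change scores: −0.29 to −0.36.
- Mixed model: −0.35 to −0.36 if discharge depends on observed values, −0.25 to −0.34 if on unmeasured state.

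**7. Which day, and which covariance.** With the full effect present by Day 3, the mixed-model variance is 26-64% lower on Day 3 than on Day 5. With only 60% of the effect reached by Day 3, Day 5 has at least equal power in 20 of 24 scenarios, by up to 28 points.

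Compound symmetry with model-based standard errors rejected a true null on Day 5 in 8.5-12.5% of trials (eight scenarios with the slope or AR(1) model, 400 trials each) and in 13-17% in two further checks of 150 trials. A likelihood model without a small-sample correction rejected 9.7%.

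**The case against.** The tests named are sound in a randomised comparison with complete data, so a reader might infer that the plan's tests are invalid; the documents do not support that. The main loss is precision.

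The plan also does not prescribe a fixed-day test: a t-test on a patient-level summary could use every draw. That stands, but no such summary is named. Since the markers are in neither endpoint list of Specific Aims, the quoted sentence may not govern them, which leaves them with less of an analysis plan, not more. Data Analysis describes the outcomes as mainly descriptive, which lowers the stakes without settling role or day.

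The scale point is ambiguity rather than contradiction, because a fall in levels can be read as a change. One week may be a loose label for Day 5, but then the text should say so and define Day 0.

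Three further inferences fail:
- **That Day 3 must be the contrast.** Its advantage depends on assuming the effect is complete by then. Preliminary Results reports no marker difference over three days in the pilot. With 14 per arm that does not rule Day 3 out, but it bears on the choice.
- **That the marker result is biased towards the drug.** The larger biases belong to raw levels, go in either direction and need discharge to depend on both marker and treatment. The Project Summary specifies change.
- **That Day 0 CRP is not collected.** Data Collection and Handling names Days 1, 3, 4 and 5 for research handling, but the schedule marks CRP as a research test on all six days. This needs only confirmation.

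**Conclusion.** The concern holds. The conflicts over role and day are plain on the text, the one-week endpoint cannot be observed as scheduled, and no analysis rule covers discharged patients. The documents do give a collection rule: sample and record until discharge.

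The size is illustrative only. Under assumed SDs, correlations and discharge patterns with 75 per arm, a baseline-adjusted longitudinal model had roughly 10-40% lower variance than a change-score t-test on Day 3, mostly from baseline adjustment, and 17-50% on Day 5. Scenarios with 64 per arm were not simulated.

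A reader might infer that the trial's main result is at risk. If the composite is primary, it is not: the loss falls on Aim 2. The plan should be changed on this point; confidence in the size is moderate at best.

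**What to change.** 1. Reconcile the Project Summary, Specific Aims, Experimental Design and Sample Size into one marker endpoint: a single role (secondary if the composite is primary), scale, defined Day 0, and a day or average over days that is actually sampled. Fix it before unblinding. The sponsor chooses the day, weighing falling numbers in hospital by Day 5 against the pilot's lack of a marker difference over three days.
2. Analyse each log-transformed marker with a likelihood-based repeated-measures model on all draws to discharge: treatment by day, Day 0 value by day, severity stratum, unstructured covariance and a small-sample degrees-of-freedom correction. Fall back to heterogeneous Toeplitz. Do not use compound symmetry with model-based standard errors.
3. Add a not-at-random sensitivity analysis that shifts post-discharge values until the conclusion changes. Keep the t-test or Wilcoxon on change scores as support.
4. If all four markers stay primary, state a multiplicity rule. Four independent tests at 0.05 give 1 − 0.95⁴ = 18.5% family-wise error.

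**Cost.** Plan wording and slightly more analysis; no new samples. The model assumes discharge depends on observed values. In the simulations where it depended on unmeasured state, the Day 3 estimate shrank 0.002-0.036 more than change scores did. Across all 24 scenarios, mean squared error was still 14-38% lower.

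### The composite that sizes the trial has no named test, and no analysis uses the severity strata of the randomisation

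*Combined protocol and SAP*

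**What the plan says.** **Sample Size** defines a binary primary outcome: "Our primary outcome will be whether the patient develops any of the following outcomes of moderate or severe AP", followed by seven components. The planning rates come from the pilot: "7.1% of the patients on pentoxifylline experienced at least one of these outcomes, compared to 28.6% of those on the placebo". The size follows: "Using a 5% 2-sided type I error, 58 patients in each group would be needed to achieve 80% power to detect the anticipated difference". The same section ends with the allocation: "We will use a randomized block design stratifying for predicted disease severity (mild, moderate, or severe").

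**Randomization** describes the allocation without strata or block size: "Randomization will be performed by the pharmacy under the direction of the study statistician, using randomized blocks" and "Randomization will occur in a block fashion".

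**Data Analysis** specifies intention to treat and mainly descriptive statistics, then assigns tests to secondary end points only: "Continuous secondary end points will be analyzed with the t-test if the data are normally distributed and the Wilcoxon Rank Sum test if non-normal" and "Analyses of dichotomous secondary end points will use either the Chi-squared test or Fisher's Exact Test comparing proportions". Kaplan-Meier is for estimating survival. The paragraph gives no test, effect measure, interval or significance level for the primary composite and does not mention the strata. No other section describes an analysis that uses them.

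**The concern.** Two things are left open.

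1. **The primary test.** The outcome that sizes the trial has no confirmatory test. If the tests listed for secondary binary end points are carried over, the choice between chi-squared and Fisher has no rule and could be made after the data are seen.
2. **The strata.** If randomisation balances the arms on a prognostic factor and the analysis ignores it, the test uses too large a variance. Type I error falls below 5% and power is lost.

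Validity is not at stake. The loss matters mainly if the true effect is smaller than the pilot's, which the pilot leaves wide open.

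**Working it through.** **1. Reproducing the plan's figure.** Inputs from Sample Size: p1 = 0.071, p2 = 0.286, difference 0.215, mean 0.1785, z = 1.960 and 0.8416.

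- Uncorrected: n = [1.960·√(2 × 0.1785 × 0.8215) + 0.8416·√(0.071 × 0.929 + 0.286 × 0.714)]² / 0.215² = (1.0614 + 0.4374)² / 0.046225 = 48.6.
- Continuity-corrected: n′ = (n/4)·[1 + √(1 + 4/(n × 0.215))]² = 12.15 × (1 + 1.1759)² = 57.5, which rounds up to 58.

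The stated 58 appears only with the correction. The sizing therefore points to a corrected or Fisher-type test, which Data Analysis does not name for this outcome.

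**2. Is a smaller effect plausible?** Preliminary Results gives 14 patients per group, so the rates are 1/14 and 4/14. The risk ratio is 0.25, and SE(log RR) = √(1/1 − 1/14 + 1/4 − 1/14) = 1.052. The 95% CI is exp(−1.386 ± 1.96 × 1.052) = 0.03 to 1.97. A halved risk (14.3% vs 28.6%) lies well inside it.

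**3. Choice of test, strata ignored** (power in %, exact binomial enumeration):

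| Per arm | Effect | Chi-squared | Corrected chi-squared | Fisher |
|---|---|---|---|---|
| 58 | 7.1 vs 28.6% | 88.9 | 82.6 | 82.7 |
| 58 | 14.3 vs 28.6% | 48.0 | 37.6 | 38.8 |
| 75 | 7.1 vs 28.6% | 95.2 | 92.2 | 92.2 |
| 75 | 14.3 vs 28.6% | 57.6 | 49.8 | 49.8 |

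At 75 per arm the open choice between chi-squared and Fisher is worth 3.0 to 7.8 points.

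**4. Ignoring the strata.** The documents give no stratum sizes or risks, so these are assumptions.

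- Mix: mild/moderate/severe 69/21/10%. The 69% echoes the 31% with moderate or severe disease among 137 consecutive patients in Significance, although that is observed, not predicted, severity.
- Placebo risks: weak 24/36/45%, moderate 20/40/65%, strong 12/60/75%, each shifted slightly on the logit scale to 28.6% overall. The severe-to-mild odds ratios are 2.6, 7.4 and 22.
- Treatment: a common within-stratum odds ratio giving 7.1% or 14.3% overall.

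The Cochran-Mantel-Haenszel (CMH) statistic, without correction, is z = Σ(T − n₁m/N) / √Σ[n₁n₀m(N − m) / (N²(N − 1))], summed over strata. T is treated events, m all events, n₁ and n₀ the arm sizes, and N their sum.

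Rejection rates in %, 75 per arm, exact balance within strata, 200,000 simulated trials per cell (Monte Carlo SE at most 0.11 points):

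| Strata | Size: chi-squared | Pilot effect: chi-squared vs CMH | Halved risk: chi-squared vs CMH |
|---|---|---|---|
| Weak | 4.6 | 95.3 vs 95.3 | 57.7 vs 58.4 |
| Moderate | 3.8 | 95.8 vs 96.3 | 58.1 vs 61.8 |
| Strong | 1.9 | 96.7 vs 98.1 | 58.8 vs 70.3 |

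The size of CMH is 4.9 to 5.0%. With a 50/30/20% mix the strong, halved-risk gain is about 8 points. For moderate strata and a halved risk, chi-squared needs about 81 per arm to match CMH at 75.

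A check by hand for moderate strata: under the null, the ratio of within-stratum to total variance is Σw·p(1 − p) / [0.286 × 0.714] = 0.1832/0.2042 = 0.897. The effective critical value is 1.960/√0.897 = 2.07, a size of about 3.85%, in line with the simulation.

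**5. If the allocation differs.** Stratified blocks of 4 or 8 with incomplete last blocks give nearly the same results: halved-risk gains of 0.7–0.8, 3.8–3.9 and 11.6–11.8 points. With unstratified blocks, chi-squared size returns to 4.9%, and CMH gains −0.2, 0.9 and 2.8 points at the pilot effect and 0.1, 3.3 and 11.8 at a halved risk.

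**6. If placebo risk is lower.** At an assumed 20%, halved to 10%, the CMH gains at 75 per arm are about 0.1, 2.8 and 8.9 points.

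**7. If the strata are not prognostic.** CMH loses about 0.2 points at 75 per arm and up to about 1.2 at 58 with stratified blocks; with unstratified blocks, up to 0.7 and 1.7.

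**The case against.** An unstratified test after stratified randomisation is valid. At the planning effect the strata are worth at most 1.4 points at 75 per arm, so what remains could be called preference. The larger losses need both a smaller effect and at least moderately prognostic strata. Nothing in the documents supports the latter, and Significance itself says that admission prediction is unreliable, which favours the weak case. The pilot was selected for predictors of severe disease whereas this trial takes all acute pancreatitis, so 28.6% may be too high, and a lower rate shrinks the gain. With a halved risk and moderate strata the trial is underpowered whichever test is used.

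All of this stands as a limit on size. The 11-point figure is an extreme and should carry little weight.

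Two further points stand only in part. The chi-squared or Fisher sentence covers secondary end points, so applying it to the composite is an extrapolation, but the alternative is no test at all. With an expected-count rule chi-squared would nearly always be chosen, but the plan gives no such rule. Likewise, the Randomization text may be just less detailed than Sample Size rather than in conflict with it. It is still the section that instructs the pharmacy, and it mentions no strata.

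None of these points supplies a test for the primary outcome, and that gap does not depend on how prognostic the strata are.

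**Conclusion.** The point holds and should be corrected; confidence is medium. The more serious part is that the sized outcome has no named test or effect measure, with 3 to 8 points of power at 75 per arm resting on an unstated choice. The second part is a loss of efficiency from unused strata: 0 to 1.4 points at the pilot effect and about 1 to 4 points at a halved risk with weak or moderate strata.

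Type I error is not inflated, the figure of 58 per group is arithmetically sound, and planned power is met at the design effect. The strata figures rest on assumed stratum shares and risks, a common within-stratum odds ratio and, unless varied above, a 28.6% placebo risk.

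**What to change.** **First, settle the primary outcome.** Project Summary names marker changes at one week, Specific Aims lists separate clinical end points, and Sample Size uses the composite. CMH suits only a binary outcome.

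**If it is the composite,** state in Data Analysis, before unblinding:

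> The composite will be compared in all randomised patients, as randomised, at two-sided 5% with a Cochran-Mantel-Haenszel test (no continuity correction) stratified by predicted severity as used at randomisation, with a Mantel-Haenszel weighted risk difference and 95% confidence interval (Sato variance).

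In the simulations this interval covered 94.2 to 95.3%. Note that the uncorrected test departs from the corrected basis of the 58 per group but still meets its 80%: simulated CMH power at 58 per arm and the pilot effect is about 88% or more.

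**Secondary end points.**

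- Binary: keep Fisher's exact test for sparse outcomes such as death, for example fewer than 10 events in total (an expected count below 5 per arm), because uncorrected CMH rejects about 9 to 12% of the time under the null with exactly 4 events. Use CMH otherwise.
- Continuous: use the van Elteren test where Wilcoxon would be used, and a linear model with arm and stratum where the t-test would be used.
- Kaplan-Meier estimation needs no change.

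**Randomization.** State whether the blocks are stratified, how predicted severity is scored, and that the stratum is recorded for each patient.

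**Cost.** Wording only, with no added patients or visits. The practical limit is timing: enrolment was planned from about July 2015, the document is dated January 2017, and analysis was due by about June 2017. The stratified analysis is possible only if the stratum used at randomisation was kept for those already enrolled. If it was not, name a single unstratified test in advance.
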